APPENDIX 1. Programming Conventions for Outputs

IQVIA OUTPUT CONVENTIONS

Outputs will be presented according to the following IQVIA output conventions.

1. ABBREVIATIONS

- ASCII American standard code for information interchange file format
- CGM Computer graphics metafile
- ODS Output Delivery System
- RTF Rich text file format

2. INTRODUCTION

This document applies to standards used for outputting tables, listings and figures. It is intended to provide specifications to guide the statistician or statistical programmer in setting up specifications for programming tables, listings and figures. These standards should be used in the absence of customer specific standards.

3. OUTPUT FILE NAMING CONVENTIONS

File names should only consist of lowercase letters, digits (0 to 9) and underscores. A period should only be used to indicate a separator between the file name and the extension. No spaces, other special characters or punctuation marks are permitted.

Output files should be in RTF format.

The program, program log and output file name should reflect the type and number of the statistical output. If this is not possible, then the output name should be at least as descriptive as possible. A prefix can be used to distinguish between a Table, Listing and Figure document ('t' for table, 'l' for listing and 'f' for figure). If there is only 1 digit in the number of the table, listing or figure in the place where 2 digits are possible, a leading zero should be added in the file name to make sorting consistent with the sequence (e.g. T14_3_01_1.RTF)

4. PAPER SIZE, ORIENTATION AND MARGINS

- The size of paper will be A4.
- The page orientation should preferably be landscape, but portrait is also permitted.
- Margins should provide at least 3 centimeters of white space all around the page, regardless of the paper size.

- The number of columns per page (linesize) should be 132 for A4.
- The number of rows per page (pagesize) should be 46 for A4.

5. FONTS

The font type 'Courier New' should be used as a default for tables and listings, with a font size of 8. The font color should be black. No bolding, underlining italics or subscripting should be permitted. Try to avoid using super-scripts, unless absolutely necessary. Single spacing should be used for all text.

Figures should have a default font of "Times Roman", "Arial", or "Courier New".

This can be achieved by using the following options in SAS for figures created using SG Procedures or GTL:

```
proc template;
  define style newfont;
    parent = styles.rtf;
    style GraphFonts from GraphFonts /
      'GraphDataFont' = ("Courier New", 10pt)
      'GraphLabelFont' = ("Courier New", 10pt)
      'GraphValueFont' = ("Courier New", 10pt)
      'GraphFootnoteFont' = ("Courier New", 10pt);
  end;
run;
ods rtf style=newfont;
```

6. HEADER INFORMATION

Headers should be defined as follows:

- The header should be placed at the top of the page (same place on each page) regardless of the size or orientation of the table or listing
- The sponsor name and protocol number should appear in rows 1 and 2, left-aligned
- The output identification number should appear in row 4, centered after a blank line in row 3
- The output title should start in row 5, centered
- The output population should appear in row 6, centered. The population should be spelled out in full, e.g. Full Analysis Set in preference to FAS.
- Row 7 should be a blank line
- Row 8 should be a continuous row of underscores ('_') (the number of underscores should equal the linesize)
- Sentence case should be used for titles

- The output titles should be designed so that they are arranged consistently through all outputs. For example, content (e.g. Vital signs) followed by metric (e.g. observed values) e.g. Vital signs – observed values.
- Titles should not contain quotation marks or footnote references
- The column headings should be underlined with a row of underscores ('_')
- Column headings spanning more than one column should be underlined and have underscores on either side of the title and should be centered
- Column headings containing numbers should be centered
- Column headings should be in proper case or sentence case
- In general, the population count should appear in the column header in the form "(N=XXX)"
- "Statistic" should be the column header over n, Mean, SE, n (%) etc.
- As a rule, all columns should have column headings if possible.

7. TABLE AND LISTING OUTPUT CONVENTIONS

General:

- The first row in the body of the table or listing should be blank
- The left hand column should start in column 1. No indenting or centering of the output should occur.
- Rounding should be done with the SAS function ROUND.
- Numbers in tables should be rounded, not truncated.
- Alphanumeric output should be left aligned.
- Numbers should be decimal point aligned, where possible.
- Whole numbers should be right aligned.
- Text values should be left aligned.
- The first letter of a text entry should be capitalized
- Listings of adverse events, concomitant medications, medical histories etc. should be sorted in chronological order, with earliest adverse event, medication or history coming first.
- The study drug should appear first in tables with treatments as columns
- All listing outputs should be sorted (preferably by Treatment, Patient Identifier [Site Number + Patient Number]).

- Do not use superscripts and subscripts
- Exponentiation will be expressed without superscripts, i.e., m² will be displayed as m2.
- The width of the entire output should match the linesize

Univariate Statistics:

- Statistics should be presented in the same order across tables (i.e., n, Mean, Std, Median, Minimum, Maximum)
- Table statistics should line up under the N part of the (N=XXX) in the table header. All decimal points should line up. If the minimum and maximum are output on one line as Minimum, Maximum then the comma should line up with the decimal point.
- If the original data has N decimal places, then the summary statistics should have the following decimal places:
 - Minimum and maximum: N
 - Mean, median and CV%: N + 1
 - Std: N + 2

Note: An exception to this rule is for demography and other baseline characteristics summaries, in which the precision of the original data can be ignored, if less decimal places suit the statistical summary better. The full decimal precision (places) will be shown in Listings in these cases.

Frequencies and percentages (n and %):

- Percent values should be reported inside parentheses, with one space between the count and the left parenthesis of the percentage. Parentheses should be justified to accept a maximum of 100.0 as a value and padded with blank space if the percent is less than 100.0. An example is given below:

77 (100.0%)
 50 (64.9%)
 1 (1.3%)

- Percentages will be reported to one decimal place, except percent <100.0% but >99.9% will be presented as '>99.9%' (e.g., 99.99% is presented as >99.9%); and percent < 0.1% will be presented as '<0.1%' (e.g., 0.08% is presented as <0.1%). Rounding will be applied after the <0.1% and >99.9% rule.

E.g. (<0.1%)
 (6.8%)
 (>99.9%)

- Percentages may be reported to 0 decimal places as appropriate (for example, where the denominator is relatively small).
- Where counts are zero, percentages will not appear in the output.

Confidence Intervals:

- As a rule, confidence intervals are output to one place more than the raw data, and standard deviations and standard errors to two places more than the raw data
- Confidence intervals should be justified so that parentheses displayed on consecutive lines of a table “line up”. However, parentheses do not have to be used.
- Boundary values of confidence intervals should be separated by a comma.
- Boundary values should be padded as necessary to accept negative values and to allow alignment of the decimal place.
- An example is given below:

-0.12, -0.10
 9.54, 12.91

Ratios:

- Ratios should be reported to one more decimal place than the original data.

Spacing:

- There must be a minimum of 1 blank space between columns (preferably 2)

Denominators:

- If a different count other than the population count is used for a denominator (within the table) to calculate percentages, there should be a row in the table that identifies that number “n”.
- Alternatively, a footnote should be included in each table with percentages to indicate the denominator for percentages.

Missing values:

- A “0” should be used to indicate a zero frequency.
- A blank or ‘-’ will be used to indicate missing data in an end-of-text table or patient listing.
- In the case that only a single value is used in the creation of summary statistics (i.e. n=1) then only n and the mean will be presented.

8. FIGURE OUTPUT CONVENTIONS

- Figures should be provided in RTF files using the SAS Output Delivery System (ODS). Formats such as Computer Graphics Metafile (CGM), PNG (Portable Network

Graphic), etc. should be used for the formatted graphical output generated by SAS.

- The CGM/PNG/etc. graphical file itself may or may not contain the title or footer.
- The image should be clear and of high quality when viewed in the Word document, and when printed.
- In general, boxes around the figures should be used.

9. FOOTNOTE INFORMATION

Footers should be defined as follows:

- A continuous line of underscores ('_') will follow the body of the table or listing prior to any footnotes at the bottom of the page
- Table footnotes should be defined using compute statements in the proc report, and should appear directly after the body of the table
- The program path and name and version number (if applicable) should appear as the last footnote at the bottom of the page
- The date/time stamp should appear directly after the program path and name
- Footnotes should be left-aligned.
- Footnotes should be in sentence case.
- Only “typewriter” symbols are permitted – e.g. “*”, “\$”, “#”, “@”, “&” and “+”.
- The choice of footnote symbols should be consistent. E.g. if you have the footnote “# indicates last observation carried forward” for one table, the same symbol and footnote should indicate LOCF for all tables.
- If text wraps across more than one line (for a note), the first letter for all lines of text after the first one will be indented to align beneath the first letter of the text in the first line (if possible)
- The page identification in the format Page X of Y (where Y is the total number of pages for the output) will appear at the bottom of the page, right aligned

Ordering of footnotes should be as follows:

- 1.) Abbreviations and definitions
- 2.) Formulae
- 3.) Symbols
- 4.) Specific notes
- 5.) Source data listing reference, if necessary

Common notes from table to table should appear in the same order.

The symbols should appear in the same order as what they are defined in the table or listing, from left to right.

10. PROGRAMMING INSTRUCTIONS

Programming instructions must appear in blue font at the end of each table or listing shell. Programming instructions, where necessary, should follow the table or listing shells in blue font, beginning with the words “Programming Note” followed by a colon. These include notes on the output, reminders of how to handle missing values, repeat shells for similar tables etc.

DATES & TIMES

Depending on data available, dates and times will take the form DDMMYY HH:MM.

SPELLING FORMAT

English US

PRESENTATION OF TREATMENT GROUPS

For all Tables and Figures, treatment groups will be based on pooling as follows. For Listings, each cohort of patients will be listed separately with screen failures appearing last:

Treatment Group	For Tables and Figures	For Listings
IMCgp100 xx mcg	Patient or Overall for Regimen 1.	Regimen 1, Parent Study = xxx: IMCgp100 xx mcg
	Shells to provide more information	

Regimen 1 = treatment on a weekly basis

PRESENTATION OF VISITS

For outputs, visits will be represented as follows and in that order:

Long Name (default)	Short Name
Screening	Scr
Baseline	BL

Long Name (default)	Short Name
Treatment Period	
Rollover Cycle 1 Day 1	RC1D1
Rollover Cycle 1 Day 8	RC1D8
Rollover Cycle 1 Day 15	RC1D15
Rollover Cycle 1 Day 22	RC1D22
Rollover Cycle 2 Day 1	RC2D1
...	...
End of Treatment record	
End of Treatment	EOT

LISTINGS

All listings will be ordered by the following (unless otherwise indicated in the template):

Parent study by ascending numeric order,

Within a Regimen and Parent study, dose cohorts (patients on same assigned dose) should be presented in ascending dose order,

center-patient ID,

visit (where applicable),

date and time (where applicable),

For listings where Screen Failures are included, these will appear in a category after the randomized/actual treatment groups labelled as 'Screen Failures'.

APPENDIX 2. Partial Date Conventions

Imputed dates will NOT be presented in the listings.

ALGORITHM FOR TREATMENT EMERGENCE OF ADVERSE EVENTS:

START DATE	STOP DATE	ACTION
Known	Known	If start date < study drug start date, then not TEAE If start date ≥ study drug start date and start date ≤ study drug end date + 90, then TEAE If start date > study drug end date + 90, then not TEAE Note: If study drug end date is missing, then as long as start date ≥ study drug start date, then TEAE
	Partial	If start date < study drug start date, then not TEAE If start date ≥ study drug start date and start date ≤ study drug end date + 90, then TEAE If start date > study drug end date + 90, then not TEAE Note: If study drug end date is missing, then as long as start date ≥ study drug start date, then TEAE
	Missing	If start date < study drug start date, then not TEAE If start date ≥ study drug start date and start date ≤ study drug end date + 90, then TEAE If start date > study drug end date + 90, then not TEAE Note: If study drug end date is missing, then as long as start date ≥ study drug start date, then TEAE
Partial, but known	Known	Not TEAE

START DATE	STOP DATE	ACTION
components (month/year or year) show that start date cannot be on or after study drug start date		
	Partial	Not TEAE
	Missing	Not TEAE
Partial, could be on or after study drug start date (i.e. same month/year or after, or year after)	Known	
If stop date < study drug start date, then not TEAE
 
If stop date ≥ study drug start date, then impute start date as earliest possible date (i.e. first day of month if day unknown or 1st January if day and month are unknown). Then, consider the following:
 
 -If start date ≤ study drug end date + 90, then TEAE -If start date > study drug end date + 90, then not TEAE 
Note: If study drug end date is missing, then as long as the imputed start date ≥ study drug start date, then TEAE

	Partial	
Impute stop date as latest possible date (i.e. last day of month if day unknown or 31st December if day and month are unknown), then:
 
If stop date < study drug start date, then not TEAE
 
If stop date ≥ study drug start date, then impute start date as earliest possible date (i.e. first day of month if day unknown or 1st January if day and month are unknown). Then, consider the following:
 
 -If start date ≤ study drug end date + 90, then TEAE

START DATE	STOP DATE	ACTION
		-If start date > study drug end date + 90, then not TEAE Note: If study drug end date is missing, then as long as the imputed start date ≥ study drug start date, then TEAE.
	Missing	Impute start date as earliest possible date (i.e. first day of month if day unknown or 1st January if day and month are unknown). Then, consider the following: -If start date ≤ study drug end date + 90, then TEAE -If start date > study drug end date + 90, then not TEAE Note: If study drug end date is missing, then as long as the imputed start date ≥ study drug start date, then TEAE.
Missing	Known	If stop date < study drug start date, then not TEAE If stop date ≥ study drug start date, then TEAE
	Partial	Impute stop date as latest possible date (i.e. last day of month if day unknown or 31st December if day and month are unknown), then: If stop date < study drug start date, then not TEAE If stop date ≥ study drug start date, then TEAE
	Missing	Assumed TEAE

Note: Study drug start date is the parent study first drug date.

ALGORITHM FOR PRIOR / CONCOMITANT MEDICATIONS:

START DATE	STOP DATE	ACTION
Known	Known	If stop date < study drug start date, assign as prior If stop date ≥ study drug start date and start date ≤ end of treatment, assign as concomitant If stop date ≥ study drug start date and start date > end of treatment, assign as post study
	Partial	Impute stop date as latest possible date (i.e. last day of month if day unknown or 31 st December if day and month are unknown), then: If stop date < study drug start date, assign as prior If stop date ≥ study drug start date and start date ≤ end of treatment, assign as concomitant If stop date ≥ study drug start date and start date > end of treatment, assign as post treatment
	Missing	If stop date is missing could never be assumed a prior medication If start date ≤ end of treatment, assign as concomitant If start date > end of treatment, assign as post treatment
Partial	Known	Impute start date as earliest possible date (i.e. first day of month if day unknown or 1 st January if day and month are unknown), then: If stop date < study drug start date, assign as prior If stop date ≥ study drug start date and start date ≤ end of treatment, assign as concomitant If stop date ≥ study drug start date and start date > end of treatment, assign as post treatment
	Partial	Impute start date as earliest possible date (i.e. first day of month if day unknown or 1 st January if day and month are unknown) and impute stop date as latest possible date (i.e. last day of month if day unknown or 31 st December if day and month are unknown), then: If stop date < study drug start date, assign as prior If stop date ≥ study drug start date and start date ≤ end of treatment, assign as concomitant If stop date ≥ study drug start date and start date > end of treatment, assign as post treatment
	Missing	Impute start date as earliest possible date (i.e. first day of month if day unknown or 1 st January if day and month are unknown), then: If stop date is missing could never be assumed a prior medication If start date ≤ end of treatment, assign as concomitant If start date > end of treatment, assign as post treatment

START DATE	STOP DATE	ACTION
Missing	Known	If stop date < study drug start date, assign as prior If stop date ≥ study drug start date, assign as concomitant Cannot be assigned as 'post treatment'
	Partial	Impute stop date as latest possible date (i.e. last day of month if day unknown or 31 st December if day and month are unknown), then: If stop date < study drug start date, assign as prior If stop date ≥ study drug start date, assign as concomitant Cannot be assigned as 'post treatment'
	Missing	Assign as concomitant

Note: Study drug start date is the parent study first drug date.

Document Approval Signature(s)

This document has been signed electronically in compliance with IQVIA and IQVIA Companies' electronic signature policies and procedures. This page is a manifestation of the electronic signatures, which may be confirmed within the IQVIA and IQVIA Companies' source system in accordance with IQVIA and IQVIA Companies' records retention policies.

Note: the Title field in the signature block has been intentionally left blank.

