## 8 ADVERSE EVENTS AND SAFETY REPORTING

### 8.1 Assessment of Safety

All patients who receive any treatment with IMCgp100 will be considered evaluable for safety. All AEs, regardless of study drug relationship, will be collected through the 90-day Safety Follow-up Period. At the time of consent, if any patient has any ongoing AE(s) from the parent IMCgp100 study, the AE(s) will be captured on the eCRF page and the "Ongoing at Start of Study" must be answered "Yes". The start date recorded in the eCRF for the rollover study should be equal to the start date of the event as recorded in the parent study. Timely, accurate, and complete reporting and analysis of safety information from clinical studies are crucial for the protection of patients and is mandated by regulatory agencies worldwide. The Sponsor and CRO have established standard operating procedures in conformity with regulatory requirements worldwide to ensure appropriate reporting of all safety information. All clinical studies conducted by the Sponsor or its affiliates will be conducted in accordance with those procedures.

Individual AEs should be evaluated by the investigator and should be reported to the CRO/Sponsor for evaluation. This includes the evaluation of the event's seriousness and the causality between the investigational medicinal product(s) and/or concomitant therapy and the AE. The CRO/Sponsor is required to maintain detailed records of all AEs reported by the investigator(s) and to perform an evaluation with respect to seriousness, causality, and expectedness. On request of a competent authority in whose territory the clinical trial is being conducted, the Sponsor should submit detailed records of all AEs which are reported by the relevant investigators. Case report processing concerns evaluation of data in individual cases, identification of individual cases requiring specific handling, recognition and processing of alerts, and any other data processing of aggregated cases.

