10.1. Derivations

- Age (years) will be derived using the following SAS code:

$$\text{floor} \left(\frac{(\text{intck}('month', \&birth, \&date) - (\text{day}(\&date) < \text{day}(\&birth)))}{12} \right)$$
 - &birth= Date of birth

- &date = (Date of informed consent)
- Note: For countries where only the year of birth is provided due to privacy laws, impute birth month and day as June 15.
- Time since primary diagnosis (years) = (Date of informed consent – Date of Primary Diagnosis + 1) / 365.25
 - Note: Partial primary diagnosis dates are imputed using 15th day of month if only month/year present or July 02 if only year present.
- Best response on any prior anti-cancer therapy for metastatic disease = the “best” *best response* as derived from the *Prior Anti-Cancer Therapy (PAT)* eCRF page, considering all medications identified from the medical review. From best to worst, the following order will be used:
 - Complete Response
 - Partial Response
 - Stable Disease
 - Progressive Disease
 - Non-Evaluable
 - Not Applicable
- BMI (kg/m²) = weight (kg) / (height (cm) / 100)²

11. Surgical and Medical History

Medical History information will be listed only.

- Medical History will be coded using Medical Dictionary for Regulatory Activities (MedDRA) central coding dictionary, using the latest version of MedDRA available at the time of coding for the reporting period.
 - Medical History conditions are defined as those conditions beginning prior to screening which stop prior to or are ongoing at Screening.
 - Presented by System Organ Class (SOC) and Preferred Term (PT).

12. Concomitant Medications

Concomitant medications and significant non-drug therapies will be presented and coded using the World Health Organization drug dictionary (WHODD), using the latest version available at the time of coding for the reporting period.

Medications will be listed by Preferred Name (coded) and by Reported Term.

See [APPENDIX 2](#) for handling of partial dates for medications. In the case where it is not possible to define a medication as prior, concomitant, or post treatment, the medication will be classified by the worst case; i.e. concomitant. (Refer to Protocol Section 6.2)

- ‘Prior’ medications are medications which started and stopped prior to the first dose of study drug of the rollover study.
- ‘Concomitant’ medications are medications which:

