15.1. Adverse Events

Patients with multiple adverse events in the same category are counted only once in that category and those with adverse events in more than 1 category are counted once in each of those categories. Adverse Events (AEs) will be coded using Medical Dictionary for Regulatory Activities (MedDRA) central coding dictionary, using the latest version of MedDRA available at the time of coding for the reporting period.

Treatment-emergent adverse events (TEAEs) are defined as AEs that started or worsened in severity from the date of first dose of the rollover study (regardless of time) up until 90 days after the last dose of study drug of this rollover study.

See [APPENDIX 2](#) for handling of partial dates for AEs. In the case where it is not possible to define an AE as treatment-emergent or not, the AE will be classified by the worst case; i.e. treatment emergent.

An overall summary of number of patients within each of the categories described in the subsection below, will be provided as specified in the templates.

An AE Listing will include TEAEs and Non-TEAEs, including those from before the first dose in the parent study and post-treatment periods which will be flagged as such. Only TEAEs will be summarized.

AE Structure as Recorded in the eCRF:

AEs will be recorded in the eCRF such that any change in severity over the course of their duration will be recorded as a single record. The AE/SAE eCRF page collects ‘Initial Grade’ and ‘Most Extreme Grade’ but not the date of the severity grade change. No further manipulation post collection is required, and the AE/SAE data will be listed as recorded.

The definition of a treatment-emergent AE will be handled for AEs that change in severity over the course of their duration, by assuming that any AE that *might have worsened* in severity within the timeframe from the date of first dose of the rollover study (regardless of time) up until 90 days after the last dose of study drug, will be defined as treatment-emergent. A worsening severity is defined as changing from a less severe (lower) CTCAE grade to a more severe (higher) CTCAE grade. For example, if an AE started prior to date of first dose of the parent study but ended on or after date of first dose of the parent study (regardless of time), and the ‘Most Extreme Grade’ is more severe (higher) than the ‘Initial Grade’, then the AE is assumed to be treatment-emergent.

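### SAP Appendix 2 dates treatment emergence from the first parent-study dose, against the rollover definition in SAP 15.1, so carried-over AEs can enter the primary AE incidence

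*SAP*

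**What the plan says.** SAP Section 15.1 defines TEAEs as "AEs that started or worsened in severity from the date of first dose of the rollover study", up to 90 days after the last rollover dose. It adds that an AE whose grade could have risen within that window is to be treated as emergent, judged by comparing Initial Grade with Most Extreme Grade. The example that follows uses the other study's dose, however: "if an AE started prior to date of first dose of the parent study but ended on or after date" of that same parent dose, with a higher extreme grade, the event is taken as emergent.

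SAP Appendix 2 gives the row-by-row algorithm. For a known start date the rules are "If start date < study drug start date, then not TEAE" and "If start date ≥ study drug start date and start date ≤ study drug end date + 90, then TEAE". A note under the table fixes the meaning of the start date: "Note: Study drug start date is the parent study first drug date". The same note stands under the medication algorithm, although SAP Section 12 defines prior medications as "medications which started and stopped prior to the first dose of study drug of the rollover study".

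Protocol Section 8.1 requires AEs ongoing at rollover consent to be recorded in the rollover eCRF. Their start date "should be equal to the start date of the event as recorded in the parent study".

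The primary variable is AE incidence (Protocol 9.5.1). SAP 15.1 restricts the AE tables to TEAEs and leaves other AEs to a flagged listing.

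**The concern.** Two sections of the SAP give incompatible rules for the flag that decides which events reach the primary table. Under Appendix 2, an event that began in the parent study and simply continued is counted as a rollover event. The table of grade 3 or higher events and the table of drug-related events inherit the same flag.

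The resulting number would have no clear meaning. Protocol 8.1 brings in only parent-study AEs still ongoing at consent, not those that had already resolved. A parent-anchored count is therefore neither the incidence during the rollover nor the cumulative incidence since first exposure. The carried-over events also belong to the parent study's own results.

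The table has a second gap. An event starting before the anchor is classed as not emergent, with no exception for worsening. If someone corrects only the date, real worsening during the rollover drops out.

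**Working it through.** There is no sample size, power or expected AE rate in the documents to reproduce. The check has two parts.

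**1. Which anchor do the documents support?**

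- Rollover dose: the SAP 15.1 definition, the SAP 6.1 reference start date (which reserves the parent dose for survival), and the SAP 15 on-treatment period.
- Rollover dose: Protocol 9.6.1, where the on-treatment period follows a pre-treatment period beginning at consent, and Protocol 9.6.1.1, which tabulates only AEs new or worsened on treatment.
- Parent dose: the Appendix 2 note and the example in SAP 15.1.
- SAP 3.3, which lists changes from the protocol, does not mention a parent anchor.

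**2. What does each rule do to the same event?** The Appendix 2 known-date rule was applied with each anchor and compared with the SAP 15.1 definition. Event dates were assumed.

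| Event | Appendix 2, parent anchor | Appendix 2, rollover anchor | SAP 15.1 |
|---|---|---|---|
| Parent AE ongoing at consent, grade 2 throughout | TEAE | not | not |
| Parent AE ongoing at consent, grade 1 to 3 | TEAE | not | TEAE |
| Onset between consent and RC1D1, not worsening | TEAE | not | not |
| Onset before first parent dose, ongoing, grade 1 to 2 | not | not | TEAE |
| Onset during rollover treatment | TEAE | TEAE | TEAE |
| Onset more than 90 days after last dose | not | not | not |

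Rows 1 and 3 show the overcount from the parent anchor. Row 2 shows what is lost if only the anchor is moved. Row 4 shows that the missing worsening branch already conflicts with 15.1 as the SAP stands.

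**Size.** Let p be the proportion of patients with a TEAE under SAP 15.1, and q the proportion with an AE ongoing at consent, assumed independent of p. In a patient with no rollover TEAE, an ongoing AE is by definition unworsened, so it adds that patient to the Appendix 2 count. Then

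reported incidence = p + (1 − p)q, and excess = (1 − p)q.

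| p | q = 0.2 | q = 0.6 | Excess (points) |
|---|---|---|---|
| 0.4 | 0.4 + 0.6×0.2 = 0.52 | 0.4 + 0.6×0.6 = 0.76 | 12 to 36 |
| 0.6 | 0.6 + 0.4×0.2 = 0.68 | 0.6 + 0.4×0.6 = 0.84 | 8 to 24 |
| 0.8 | 0.8 + 0.2×0.2 = 0.84 | 0.8 + 0.2×0.6 = 0.92 | 4 to 12 |

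Both p and q are assumptions; the documents give neither.

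**Medications.** A drug started and stopped during the parent study is prior under SAP Section 12. Under Appendix 2 it is concomitant, because its stop date falls after the parent start date and its start date before end of treatment. SAP 12.1 flags prohibited therapies in the concomitant listing and refers to this algorithm, so parent-period drugs could be flagged wrongly.

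**The case against.** The best defence is that the definition in 15.1 governs. Appendix 2 is titled as a set of partial-date conventions, 15.1 refers to it only for that purpose, and most of the surrounding text uses the rollover dose. A careful programmer would follow 15.1, including its rule on worsening, and nothing would go wrong. The output shells, which might settle the matter, are not available. It is true that the overcount arises only if Appendix 2 is followed. But Appendix 2 is the only stepwise TEAE rule in the SAP, its rows classify complete dates, and the example in 15.1 repeats its anchor, so the intended reading cannot be taken for granted.

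The size is also open to challenge. Independence of p and q is an assumption, and true incidence may exceed 80%, since all AEs are collected regardless of relationship. With q = 0.6 the excess is 0.1×0.6 = 6 points at p = 0.9 and 0.05×0.6 = 3 points at p = 0.95. This stands: the range is an illustration, not a bound.

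Three smaller points are fair. The study is descriptive and all AEs are listed, so the count could be rebuilt. The gap between consent and RC1D1 can be nil, because screening and first dose may fall on the same day. The medication anchor affects listings, not an endpoint. None of these removes the conflict in the primary table.

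**Conclusion.** The SAP is wrong as written and must be corrected before the analysis is programmed. Its TEAE algorithm contradicts its TEAE definition, and the difference falls directly on the primary variable. Following Appendix 2 counts unworsened carried-over AEs, and unworsened AEs between consent and first rollover dose, as rollover events. The excess is 4 to 36 percentage points over p = 40% to 80% and q = 20% to 60% under independence, and smaller if true incidence is higher. The classification conflict itself rests on no assumed rate. Correcting the date alone would, under the Appendix 2 rows, miss every carried-over AE with a known start date that worsened in the rollover.

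**What to change.** Make these changes together, since a partial correction creates a new error:

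1. In both Appendix 2 notes, define study drug start date as the date of first IMCgp100 dose in the rollover study (RC1D1).
2. In the SAP 15.1 example, replace the parent study with the rollover study. In the same section, reword the listing sentence so that non-TEAEs are flagged relative to the first rollover dose; unworsened carried-over AEs then stay visible there.
3. In the Appendix 2 rows where the start date, known or partial, precedes RC1D1, replace the flat exclusion with this rule: if the stop date is on or after RC1D1 or the AE is ongoing, and Most Extreme Grade exceeds Initial Grade, then TEAE; otherwise not TEAE. For partial stop dates, apply the latest-possible-date imputation already used elsewhere in the table. Where the status remains unclear, the worst-case default in 15.1 applies.

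The cost is SAP wording and a few lines of derivation code. Both grades are already collected, so no new data are needed. The reported incidence may change.
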